**Inclusion Criteria:**

- 1) Patients in the Tianjin regional database from 01/01/2015 to 31/12/2019.
- 2) Group A: patients with diagnosis of diabetes, and with diagnosis of cardiovascular disease, heart failure, chronic kidney disease or at high cardiovascular risk;
- 3) Group B: patients with diagnosis of diabetes, but not with diagnosis of cardiovascular disease, heart failure, chronic kidney disease or at high cardiovascular risk;
- 4) Group C: patients with diagnosis of cardiovascular disease, heart failure, chronic kidney disease or at high cardiovascular risk, but not with diagnosis of diabetes;
- 5) Group D: patients without diagnosis of cardiovascular disease, heart failure, chronic kidney disease or at high cardiovascular risk, and without diagnosis of diabetes. We will randomly select a group of non-diabetic patients without any of the above diseases by matching on age and gender.

**Definition of diabetes, cardiovascular disease, chronic kidney disease and high cardiovascular risk:**

- Diabetes: patients with at least 1 discharged diagnosis or 2 outpatient diagnosis of diabetes (the first diagnosis will be the index diagnosis, and the time interval between diagnoses is not restricted) (International classification of disease (ICD)-10 E10-E14)
- Cardiovascular disease: patients with at least 1 discharged diagnosis or 2 outpatient diagnosis of ischemic heart diseases (the first diagnosis will be the index diagnosis, and the time interval between diagnoses is not restricted) (ICD-10 I20-I25); or patients with at least 1 discharged diagnosis or 2 outpatient diagnosis of cerebrovascular diseases (the first diagnosis will be the index diagnosis, and the time interval between diagnoses is not restricted) (ICD-10 I60-I69); or patients with at least 1 discharged diagnosis or 2 outpatient diagnosis of ischemic peripheral artery disease (the first diagnosis will be the index diagnosis, and the time interval between diagnoses is not restricted) (ICD-10 E10.501, E11.603, E14.501, E14.606, E14.503, I73.9, I99.03, I99.04);
- Heart failure: patients with at least 1 discharged diagnosis or 2 outpatient diagnosis of heart failure (the first diagnosis will be the index diagnosis, and the time interval between diagnoses is not restricted) (ICD-10 I50);
- Chronic kidney disease: inpatients with at least once 1 discharged diagnosis CKD (ICD-10 N18), or inpatients with the last estimated glomerular filtration rate (eGFR, calculated by CKD-EPI equation) <60 mL/min/1.73 m^2 or prescription of dialysis, but not with the diagnosis of acute kidney injury (ICD-10 N17); or outpatients with at least 2 diagnosis of CKD (the first diagnosis will be the index diagnosis, and the time interval between diagnoses is not restricted) or with two consecutive eGFR (calculated by CKD-EPI equation) <60 mL/min/1.73 m^2 by 90 days or more.
- High cardiovascular risk: patients with at least 1 discharged diagnosis or 2 outpatient diagnosis of hypertension (the first diagnosis will be the index diagnosis, and the time interval between diagnoses is not restricted) (ICD-10 I10-I15); or at least 1 discharged diagnosis or 2 outpatient diagnosis of hyperlipidemia (ICD-10 E78.001-E78.003, E78.101, E78.203, E78.301-E78.304, E78.306, E78.401, E78.501, E78.902)

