#### **Inclusion Criteria:**

- 1) Patients in the Tianjin regional database from 01/01/2015 to 31/12/2019.
- 2) Group A: patients with diagnosis of diabetes, and with diagnosis of cardiovascular disease, heart failure, chronic kidney disease or at high cardiovascular risk.
- 3) Group B: patients with diagnosis of diabetes, but not with diagnosis of cardiovascular disease, heart failure, chronic kidney disease or at high cardiovascular risk.
- 4) Group C: patients with diagnosis of cardiovascular disease, heart failure, chronic kidney disease or at high cardiovascular risk, but not with diagnosis of diabetes.
- 5) Group D: patients without diagnosis of cardiovascular disease, heart failure, chronic kidney disease or at high cardiovascular risk, and without diagnosis of diabetes. We will randomly select a group of non-diabetic patients without any of the above diseases by matching on age and gender.

Definition of diabetes, cardiovascular disease, chronic kidney disease and high cardiovascular risk:

- Diabetes: patients with at least 1 discharged diagnosis or 2 outpatient diagnosis of diabetes (the first diagnosis will be the index diagnosis, and the time interval between diagnoses is not restricted) (International classification of disease (ICD)-10 E10-E14)
- Cardiovascular disease: patients with at least 1 discharged diagnosis or 2 outpatient diagnosis of ischemic heart diseases (the first diagnosis will be the index diagnosis, and the time interval between diagnoses is not restricted) (ICD-10 I20~I25); or patients with at least 1 discharged diagnosis or 2 outpatient diagnosis of cerebrovascular diseases (the first diagnosis will be the index diagnosis, and the time interval between diagnoses is not restricted) (ICD-10 I60~I69); or patients with at least 1 discharged diagnosis or 2 outpatient diagnosis of ischemic peripheral artery disease (the first diagnosis will be the index diagnosis, and the time interval between diagnoses is not restricted) (ICD-10 E10.501, E11.603, E14.501, E14.606, E14.503, I73.9, I99.03, I99.04);

- Heart failure: patients with at least 1 discharged diagnosis or 2 outpatient diagnosis of heart failure (the first diagnosis will be the index diagnosis, and the time interval between diagnoses is not restricted) (ICD-10 I50).

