- Chronic kidney disease: inpatients with at least once 1 discharged diagnosis CKD (ICD-10 N18), or inpatients with the last estimated glomerular filtration rate (eGFR, calculated by CKD-EPI equation) <60 mL/min/1.73 m^2 or prescription of dialysis, but not with the diagnosis of acute kidney injury (ICD-10 N17); or outpatients with at least 2 diagnosis of CKD (the first diagnosis will be the index diagnosis, and the time interval between diagnoses is not restricted) or with two consecutive eGFR (calculated by CKD-EPI equation) <60 mL/min/1.73 m^2 by 90 days or more.
- High cardiovascular risk: patients with at least 1 discharged diagnosis or 2 outpatient diagnosis of hypertension (the first diagnosis will be the index diagnosis, and the time interval between diagnoses is not restricted) (ICD-10 I10-I15); or at least 1 discharged diagnosis or 2 outpatient diagnosis of hyperlipidemia (ICD-10 E78.001-E78.003, E78.101, E78.203, E78.301-E78.304, E78.306, E78.401, E78.501, E78.902)

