**9.3.2.1 Primary outcomes**

1. The proportion of diabetic/non-diabetic patients with established cardiovascular disease, or chronic kidney disease, or at high cardiovascular risk.
2. The proportion of diabetic patients with established cardiovascular disease, or chronic kidney disease, or at high cardiovascular risk among all diabetic patients.
3. The proportion of non-diabetic patients with established cardiovascular disease, or chronic kidney disease, or at high cardiovascular risk among all non-diabetic patients.

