### **9.7.1 Main analysis**

Before analyses start, 200 randomly selected medical chart will be fully reviewed by well-trained experts to validate the accuracy and sensibility of code used to identify patients with cardiovascular disease or at high cardiovascular risk, chronic kidney disease and type 2 diabetes. This QC procedure for database study would be performed by [REDACTED].

The analyses will mainly describe the patient demographic characteristics, comorbidities, treatment pattern and economic burden based on 40 hospitals EMRs of Tianjin regional database. Descriptive data will be provided. The statistical methods and analyses will be described in detail in a Statistical and Epidemiological Analysis Plan (SEAP) prior to the commencement of any analyses.

Characteristics presented as continuous data will be summarized through means, standard deviations, medians, minimum and maximum values, whereas, categorical data will be summarized as counts and proportions.

All tests will be two-sided unless otherwise specified

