### **9.9 LIMITATIONS OF THE RESEARCH METHODS**

There is no unique ICD code for cardiovascular disease, CKD or at high cardiovascular risk. Each of those diseases has more than one ICD code in the medical charts. The subjects came from different hospitals; the understanding of ICD code may be different according to different hospitals.

The study is limited in representativeness and generalizability. Of 600,000 patients, only 100,000 patients contained comprehensive information about patients' basic information, medical advice, diagnosis, laboratory examination, medical records and medical costs.

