6.3 STUDY POPULATION

Diabetic/non-diabetic patients with/without established cardiovascular disease, chronic kidney disease, or at high cardiovascular risk.

Inclusion Criteria:

- 1) Patients in the Tianjin regional database from 01/01/2015 to 31/12/2019.
- 2) Group A: patients with diagnosis of diabetes, and with diagnosis of cardiovascular disease, heart failure, chronic kidney disease or at high cardiovascular risk;
- 3) Group B: patients with diagnosis of diabetes, but not with diagnosis of cardiovascular disease, heart failure, chronic kidney disease or at high cardiovascular risk;
- 4) Group C: patients with diagnosis of cardiovascular disease, heart failure, chronic kidney disease or at high cardiovascular risk, but not with diagnosis of diabetes;
- 5) Group D: patients without diagnosis of cardiovascular disease, heart failure, chronic kidney disease or at high cardiovascular risk, and without diagnosis of diabetes. We will randomly select a group of non-diabetic patients without any of the above diseases by matching on age and gender.

Definition of diabetes, cardiovascular disease, chronic kidney disease and high cardiovascular risk

- Diabetes: patients with at least 1 discharged diagnosis or 2 outpatient diagnosis of diabetes (ICD-10 E10-E14)
- Cardiovascular disease: patients with at least 1 discharged diagnosis or 2 outpatient diagnosis of ischemic heart diseases (ICD-10 I20~I25); or patients with at least 1 discharged diagnosis or 2 outpatient diagnosis of cerebrovascular diseases (ICD-10 I60~I69); or patients with at least 1 discharged diagnosis or 2 outpatient diagnosis of ischemic peripheral artery disease (ICD-10 E10.501, E11.603, E14.501, E14.606, E14.503, I73.9, I99.03, I99.04);
- Heart failure: patients with at least 1 discharged diagnosis or 2 outpatient diagnosis of heart failure (ICD-10 I50);
- Chronic kidney disease: inpatients with at least once 1 discharged diagnosis CKD (ICD-10 N18), or inpatients with the last estimated glomerular filtration rate (eGFR, calculated by CKD-EPI equation) <60 mL/min/1.73 m² or prescription of dialysis, but not with the diagnosis of acute kidney injury (ICD-10 N17); or outpatients with at least 2 diagnosis of CKD or with two consecutive eGFR (calculated by CKD-EPI equation) <60 mL/min/1.73 m² by 90 days or more.

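### The peripheral artery disease code list accepts I73.9 but not I70.2, so patients whose only cardiovascular evidence is limb-artery atherosclerosis are left out of the cardiovascular disease rows

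*Protocol*

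**What the plan says.** Protocol 9.2.2 counts as cardiovascular disease the ischemic heart disease range I20 to I25, the cerebrovascular range I60 to I69, and "patients with at least 1 discharged diagnosis or 2 outpatient diagnosis of ischemic peripheral artery disease". The third route is defined only by the codes "ICD-10 E10.501, E11.603, E14.501, E14.606, E14.503, I73.9, I99.03, I99.04". SAP 6.3 repeats the list unchanged: "ischemic peripheral artery disease (ICD-10 E10.501, E11.603, E14.501, E14.606, E14.503, I73.9, I99.03, I99.04". There is no procedure, imaging or treatment route to peripheral artery disease, and neither document gives a reason for the choice of codes.

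The other conditions that place a patient in Group A or C are heart failure (I50), CKD ("inpatients with at least once 1 discharged diagnosis CKD (ICD-10 N18", plus eGFR and dialysis rules), hypertension (I10 to I15) and a selected set of lipid codes ("ICD-10 E78.001-E78.003, E78.101, E78.203, E78.301-E78.304, E78.306, E78.401, E78.501, E78.902").

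These definitions feed the primary outcomes in Protocol 9.3.2.1, for example "The proportion of diabetic patients with established cardiovascular disease, or chronic kidney disease, or at high cardiovascular risk among all diabetic patients". SAP Table 1 also reports cardiovascular disease in its own row within Group A and within Group C.

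**The concern.** Heart and cerebrovascular disease are captured by whole ICD-10 ranges, but limb-artery disease by a short selection. The selection takes the unspecified code I73.9 and leaves out the specific code for limb atherosclerosis, I70.2. The more exact the coding, the less likely the patient is to count as having ischemic peripheral artery disease, which is the condition the plan names.

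Two results are at stake. The cardiovascular disease rows of SAP Table 1 would be too low by the number of patients whose only cardiovascular evidence is I70.2. In addition, some patients with arterial disease would enter Group B or the pool for Group D, both described as free of cardiovascular disease. The loss would also depend on local coding habit: a hospital that prefers I70.2 to I73.9 would show less disease. Protocol 9.9 concedes that "the understanding of ICD code may be different according to different hospitals", but it does not mention missing codes or a correction.

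**Working it through.** The plan states no figure on this point, so the first check is one of coverage. The meaning of I70.2 is taken from ICD-10, the classification the plan adopts; the documents do not print it.

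**Step 1. Is I70.2 covered anywhere?** The code was compared with every code and range in Protocol 9.2.2 and SAP 6.3.

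| Definition | Codes | Covers I70.2? | Covers I73.9 (control)? |
|---|---|---|---|
| Diabetes | E10 to E14 | no | no |
| Ischemic heart disease | I20 to I25 | no | no |
| Cerebrovascular disease | I60 to I69 | no | no |
| Peripheral artery disease | eight listed codes | no | yes |
| Heart failure | I50 | no | no |
| CKD | N18 | no | no |
| Hypertension | I10 to I15 | no | no |
| Hyperlipidemia | listed E78 codes | no | no |

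The only code listed between I70 and I79 is I73.9.

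**Step 2. Who is affected?** A patient is lost from the cardiovascular row only with I70.2 and no qualifying I20 to I25, I60 to I69 or listed peripheral diagnosis. A patient moves from Group A to Group B, or from Group C to the Group D pool, only if heart failure, CKD, hypertension and listed hyperlipidemia are absent as well.

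**Step 3. Is the effect the same in both populations?** Five of the eight codes (E10.501, E11.603, E14.501, E14.606, E14.503) lie within E10 to E14. Anyone who meets the one-discharge or two-outpatient rule on those codes also meets the plan's diabetes rule. A non-diabetic patient can therefore qualify only through I73.9, I99.03 or I99.04. At most, a single outpatient E-code could be one of two outpatient diagnoses alongside one of those three. Diabetic patients have additional routes, so the loss may differ between the populations.

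**Step 4. Possible size among diabetic patients.** All three inputs are assumptions:
- f, the share of diabetic patients carrying I70.2: 1% to 5%
- u, the share of those carriers with no other listed cardiovascular code: 30% to 50%
- v, the share of those carriers with no other qualifying condition of any kind: 5% to 15%

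Shortfall in the cardiovascular row = f × u: 0.01 × 0.30 = 0.3 points, up to 0.05 × 0.50 = 2.5 points. Per 100,000 patients (the Protocol's number with comprehensive information) this is 300 to 2,500.

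Shortfall in the composite = f × v: 0.01 × 0.05 = 0.05 points, up to 0.05 × 0.15 = 0.75 points.

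For scale, the standard error of a 50% proportion in 100,000 patients is √(0.25/100,000) = 0.158 points. The lower row shortfall exceeds this; the lower composite shortfall does not.

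**Step 5. Would the chart review find it?** If 0.3% of reviewed patients were affected, 200 random charts would contain none with probability 0.997^200 = 0.55. If 2.5% were affected, the probability would be 0.975^200 = 0.006.

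**The case against.** The documents contain no internal contradiction: the same eight codes stand in both. The list uses local extensions, such as I99.03 and I99.04, that the documents do not define, and some limb ischemia may be recorded there. The primary outcomes as worded are composites, and most patients with limb atherosclerosis may qualify through another condition. The plan also provides a check before analysis: "200 randomly selected medical chart will be fully reviewed by well-trained experts to validate the accuracy and sensibility of code used".

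These points limit the size, not the existence, of the gap. Whatever I99.03 and I99.04 hold, a patient coded I70.2 still fails the rule as written. The chart review is a real safeguard, but neither document says the list will be revised on its result or which patients the charts are drawn from. At the low end of the assumed range it would more likely than not contain no such patient.

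A reader might infer more than the documents support:
- **All patients with limb atherosclerosis are counted as free of cardiovascular disease.** Not so: any qualifying listed cardiovascular diagnosis keeps the patient in the row.
- **Diabetic and non-diabetic patients are affected alike.** The make-up of the list argues against assuming this.
- **The omission of I74 is the same error.** I74 is arterial embolism and thrombosis in general. Whether its limb codes belong under ischemic peripheral artery disease is a matter of definition.
- **A known number of patients is misclassified.** No frequency is given, and head counts depend on both the assumed shares and the chosen denominator.

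**Conclusion.** The point holds in a limited form. As written, the definition accepts I73.9 and rejects I70.2, and no other listed code or range recovers patients whose only cardiovascular evidence is I70.2. They are omitted from the SAP Table 1 cardiovascular rows, and those with no other qualifying condition enter Group B or the Group D pool.

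The direction is certain: the cardiovascular rows can only be too low. The size cannot be derived from the documents and is probably small for the composite. The ranges in the working rest wholly on assumed shares. Non-diabetic patients have fewer coding routes, so the contrast between the two populations could also shift, but the documents do not show by how much. The change is worth making before extraction; it does not undermine the design.

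**What to change.** In Protocol 9.2.2 and SAP 6.3, add I70.2 with all its extensions to the peripheral artery disease list, under the existing rule of one discharge or two outpatient diagnoses. Rebuild Groups A to D, including the matched sample for Group D. Report the SAP Table 1 cardiovascular rows under both the present and the extended list, separately for diabetic and non-diabetic patients, so that a count replaces the assumed size. Show the limb-artery codes I74.3 and I74.4 only as a sensitivity count, outside the main definition.

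The cost is one line in each document and one code family in the extraction query; the diagnosis field is already among the variables in Protocol 9.3, Table 1. The drawback is a slightly higher cardiovascular proportion that is less comparable with any earlier use of the same list, which reporting both lists offsets.

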**Reason(s) for change 4:**

To be consistent with the further outcome

CHANGE 5: Clarified the method how to protect patient privacy
Section of the Clinical Trial Protocol: 10.2
The study will use de-identified data which contains a significant level of protection against the release of personal information to outside entities. Informed patient consent could be waived. BI will not access data at individual level, but only aggregate results will be obtained.
Was changed to:
The study will use MD-5 to de-identify personal information in the data including names, ID-numbers, visit numbers, home addresses, etc. against the release of personal information to outside entities. Informed patient consent could be waived. BI will not access data at individual level, but only aggregate results will be obtained.
Reason(s) for change 5:
Clarified the method how to protect patient privacy
CHANGE 6: Specified the time period of data source
Section of the Clinical Trial Protocol: full text
...Tianjin regional database from 2015 to 2019...
Was changed to:
...Tianjin regional database from 01/01/2015 to 31/12/2019...
Reason(s) for change 6:
Specified the time period of data source

## Amendment 2:

CHANGE 1: Amended the study title according to the objectives
Section of the Clinical Trial Protocol: Cover page and 4
Title: Characteristics, treatment, and economic burden of disease of Chinese diabetic/non-diabetic patients with/without established cardiovascular disease, chronic kidney disease, or at high cardiovascular risk Brief lay title: Clinical Characteristics and economic burden of Chinese diabetic/non-diabetic patients with/without established cardiovascular disease, chronic kidney disease, or at high cardiovascular risk
Was changed to:
Title: Clinical characteristics and disease burden of patients with diabetes mellitus combined with cardiovascular or chronic kidney disease based on regional medical database in Tianjin China Brief lay title: Clinical characteristics and disease burden of diabetic patients based on Tianjin regional database
Reason(s) for change 1:
Amended the study title according to the objectives and the study database
CHANGE 2: Specified the criteria for grouping and indicator details
Section of the Clinical Trial Protocol: 9.3
None
Was changed to:
The following variables will be collected in this study. 1) Demographic characteristics of the patients: age, gender, type of health insurance, etc. 2) Status of the patient's disease diagnosis: outpatient diagnosis, discharge diagnosis. 3) Information on the patient's laboratory tests, glycated haemoglobin, blood glucose,

blood creatinine, estimated glomerular filtration rate, urine microalbumin, lipids, etc.  
 4) Patient medication and treatment: including CVD-related treatment (antiplatelet agents, statins, vasodilators), diabetes-related treatment (insulin, oral hypoglycaemic agents), hypertension-related treatment (e.g. calcium antagonists, angiotensin-converting enzyme antagonists, angiotensin receptor antagonists, beta-receptor antagonists, etc.), hyperlipidaemia-related treatment (e.g. lipid-lowering drugs), CKD-related treatment (e.g., dialysis, angiotensin-converting enzyme antagonists, angiotensin receptor antagonists, kidney transplantation), etc.  
 5) Number of days the patient was hospitalized  
 6) Patient's medical costs, including all costs during hospitalization (hospitalization, drugs, surgery, etc.)

Table 1. variables collected from database

...

Reason(s) for change 2:

Specified the criteria for grouping and indicator details

**CHANGE 3: Updated the milestones based on the current progress**

Section of the Clinical Trial Protocol: 4 & 6

- EC approval	05/2021
- Start of data collection	06/2021
- End of data collection	07/2021
- Final results	10/2021
- Final NIS report	12/2021

*Was changed to:*

- EC approval	06/2021
- Start of data collection	07/2021
- End of data collection	08/2021
- Final results	10/2021
- Final NIS report	12/2021

Reason(s) for change 3:

Updated based on the current progress

**CHANGE 4: Updated the version & date of DMRP and SEAP**

Section of the Clinical Trial Protocol: ANNEX 1

Number	Document Reference Number	Date	Title
1	To be determined	To be determined	Data Management Review Plan (DMRP)
2	To be determined	To be determined	Statistical and Epidemiological Analysis Plan (SEAP)

*Was changed to:*

Number	Document Reference Number	Date	Title
1	Not applicable	21 May 2021, Version 1.0	Data Management Review Plan (DMRP)
2	Not applicable	13 May 2021, Version 1.0	Statistical and Epidemiological Analysis Plan (SEAP)
Reason(s) for change 4:			
The DMRP and SEAP is now approved so have a valid version and date			

